5.3. Subject Groups

For analyses based on the SAF analysis set or the PK analysis set, subjects will be grouped for analyses according to the actual treatment received. For all other analyses, subjects will be grouped for analyses according to randomized treatment assignment from the double-blind treatment period.

5.4. Multiple Comparisons

Adjustments for multiple comparisons for the primary efficacy endpoints list in Section 9.2 will be performed using a fixed, sequential testing procedure. The order of the testing sequence is specified in Section 9.2. The first test in the sequence will be performed at a significance level of 0.05. If that test is significant, then the second test in the sequence will be performed at a significance level of 0.05, and so on. Testing will stop when a non-significant test occurs in order to maintain a family-wise error rate of alpha=0.05.

There will be no adjustments for multiple comparisons for the secondary efficacy or OLE endpoints.

5.5. Missing Data

In general, values for missing data will not be imputed, except as noted.

If there are no missing data, other than COVID-19-related missing values (which are handled as described previously in this SAP), or if there is a single subject with missing data, the following missing data conventions are deemed unnecessary. For a single subject, the latest available value will be used as the response value of interest.

In the event that more than one subject has missing data, the following missing data methodologies will be followed:

For the primary endpoints, missing values for post-baseline assessments will be imputed using the method of multiple imputation (MI). As a sensitivity analysis, last observation after baseline carried forward (LOCF) will be used to impute the missing value.

Post-baseline values that are missing will be imputed for each primary efficacy endpoint using the Markov Chain Monte Carlo (MCMC) method. Ten copies of the dataset with a monotonic missing pattern will be generated using the monotone data augmentation method, to impute the amount of missing data that is required to make the missing data pattern monotone before applying the multiple imputation algorithm. This method uses a non-informative Jeffery's prior to derive the posterior mode from the expectation-maximization algorithm as starting values for the MCMC method. For each of the 10 monotonic missing pattern datasets, an additional 10 datasets will be imputed to replace missing values at scheduled visits for a total of 100 datasets. These datasets will be generated using a monotone regression-based multiple imputation model. For subjects with complete data up to a particular visit, a multiple regression model will be fit that includes the outcome at that visit as the dependent variable and outcomes at previous visits, treatment group, baseline age, gender, time from disease onset, concomitant medications and duration of use, and baseline outcome as independent variables. Using these regression models, a missing value for a subject at a particular visit will be imputed as a draw from the predictive distribution given the outcomes at previous visits (some possibly imputed), the treatment group, age, gender, time from disease onset, concomitant medications and duration of use, and the baseline value.

The SAS MI procedure (ie PROC MI) will be used. The ROUND option will be used to round the imputed values to the same precision as the observed values and the minimum value for imputed will be specified as zero to avoid negative values. The seed to be used for generating the monotonic missing pattern datasets will be 0518, the seed to be used for the regression-based MI will be 0519. The analysis of covariance (ANCOVA) or rank analysis, and the mixed model repeated measures (MMRM) will be performed separately for each of the 100 complete analysis data sets, and the results will be combined into one multiple

imputation inference (estimated treatment effect and associated confidence interval and p value), using PROC MIANLALYZE.

Missing individual items or questions from the QMG scale, MGC scale, the MG-ADL questionnaire, and the MG-QOL15r scale will be imputed using the method of LOCF if no more than 2 questions are missing for QMG scale, MGC scale and MG-QOL15r scale, or no more than 1 question in MG-ADL questionnaire is missing. Otherwise, the individual score and the corresponding total score will be treated as missing.

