### 6.2. Inclusion Criteria

A participant will be eligible for inclusion in this study only if all of the following criteria apply:

1. Male or female  $\geq 18$  years of age.
2. Myasthenia Gravis Foundation of America (MGFA) Class II-IVa and likely not in need of a respirator for the duration of the study as judged by the Investigator.
3. Positive serologic test for anti-AChR antibodies at the screening visit and at least 1 of the following:
  - a. History of abnormal neuromuscular transmission test demonstrated by single-fiber-electromyography or repetitive nerve stimulation OR
  - b. History of positive edrophonium chloride test OR
  - c. Participant has demonstrated improvement in MG signs on oral cholinesterase inhibitors as assessed by the treating physician.
4. QMG score  $\geq 12$  at Screening and Baseline.
5. Stable dose of MG treatment prior to randomization. For participants receiving AZA, other non-steroidal immunosuppressive agents, steroids, and/or cholinesterase inhibitors as concomitant medications the following conditions will apply:
  - a. AZA: treatment initiated at least 12 months ago and no dose changes in the last 6 months before Screening.

- b. Other immunosuppressive treatment (e.g., methotrexate, cyclosporine, mycophenolate mofetil, and cyclophosphamide) initiated at least 6 months ago and no dose changes in the last 3 months before Screening.
  - c. Stable dose of steroid treatment at least 6 weeks before Baseline.
  - d. Cholinesterase inhibitors: stable dose for >1 week before Screening. Note: cholinesterase inhibitors must be held for at least 12 hours consistent with the revised manual for the QMG test as recommended by the MGFA, before the QMG and MGC assessments.
6. A female participant is eligible to participate if she is of:
- a. Non-childbearing potential defined as pre-menopausal females with a documented bilateral tubal ligation, bilateral oophorectomy (removal of the ovaries) or hysterectomy; hysteroscopic sterilization, or postmenopausal defined as 12 months of spontaneous amenorrhea [in questionable cases a blood sample with simultaneous follicle stimulating hormone (FSH) in the post-menopausal range is confirmatory].

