9. EFFICACY ANALYSES

9.1. Definition of the Primary Efficacy Endpoint

The primary efficacy endpoints include:

- Percentage change from baseline in total IgG at Week 7.

Supportive variables to the primary efficacy laboratory variable are:

- Percentage change from baseline in IgG1 at Week 7
- Percentage change from baseline in IgG2 at Week 7
- Percentage change from baseline in IgG3 at Week 7
- Percentage change from baseline in IgG4 at Week 7
- Percentage change from baseline in anti-AChR-IgG level at Week 7

Percentage change from baseline will be calculated as:

$$\% \Delta = \left[100 \times \left(\frac{\text{Week 7} - \text{Baseline}}{\text{Baseline}} \right) \right]$$

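### SAP 5.5 does not name the imputed variable and uses an apparently raw scale with a zero floor; if multiple imputation is triggered and covers anti-AChR-IgG, imputed reductions are understated for low-titre participants

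*SAP*

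**What the plan says.** **Trigger.** SAP 5.5: "In the event that more than one subject has missing data, the following missing data methodologies will be followed". For a single participant the latest available value is used, and COVID-related gaps follow the separate rule in SAP 2. SAP 2 reports one missed Week 7 visit, due to a site closure, and no withdrawals.

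**Method.** SAP 5.5: "Post-baseline values that are missing will be imputed for each primary efficacy endpoint using the Markov Chain Monte Carlo (MCMC) method". After the pattern is made monotone, "These datasets will be generated using a monotone regression-based multiple imputation model", with earlier visits, arm, baseline outcome and several other covariates as predictors. A rounding instruction matches imputed results to the decimal places of the recorded data. The floor is given in these words: "the minimum value for imputed will be specified as zero to avoid negative values". No log or other transformation is mentioned for any analyte.

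**Endpoints.** SAP 9.1 gives the primary endpoint as "Percentage change from baseline in total IgG at Week 7". It lists "Percentage change from baseline in anti-AChR-IgG level at Week 7" among the supportive variables. SAP 8.3 names anti-AChR-IgG in the primary endpoint, and SAP 5.4 takes its primary endpoints from 9.2, where anti-AChR-IgG is H03 (680 mg) and H04 (340 mg), ahead of MG-ADL.

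**Titre at entry.** Protocol 6.2 asks for a "Positive serologic test for anti-AChR antibodies at the screening visit" and sets no titre limits.

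**Fallback.** SAP 9.3 advances rank analogues to primary if the ANCOVA assumptions are judged unwarranted.

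**The concern.** A reduction is a negative percent change, so a minimum of zero on that variable would be impossible to reconcile with the expected drug effect. On levels the floor is at least coherent, but it points to a scale problem. A normal model with one residual SD is fitted to concentrations that may differ several-fold between participants. High-titre participants set that SD. For a low-titre participant the draws then spread well beyond the plausible range, the negative ones are excluded and the large positive ones stay. Division by a small baseline turns these into apparent increases. With 7 participants per arm, one or two such values can raise the arm mean and inflate the pooled standard error of H03 and H04, which stand before MG-ADL in the fixed sequence.

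**Working it through.** The plan gives no figure for the imputation, so there is none to reproduce.

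**1. Percent-change reading.** Protocol 3.2.2 expects total IgG reductions of 75-80% (680 mg) and 65-70% (340 mg). SAP 1.3 assumes an SD of 20. For a true mean of -80, a normal draw restricted to zero or above has mean -80 + 20 × φ(4)/[1 - Φ(4)] = -80 + 20 × 4.226 = +4.5. The arm mean becomes

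- one of 7 imputed: (6 × -80 + 4.5)/7 = -67.9
- two of 7 imputed: (5 × -80 + 9.0)/7 = -55.9

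**2. Level reading: mechanism.** Let r be the predicted Week 7 level and s the predictive SD, both as fractions of the participant's own baseline. If negative draws are redrawn (the SAP does not say; setting them to zero also biases upward, by less), the mean imputed percent change is 100 × [r + s × φ(r/s)/Φ(r/s) - 1].

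| Case | r | s | Mean imputed change | Without floor |
|---|---|---|---|---|
| Total IgG, 2.2 of an assumed 10 g/L | 0.22 | 0.1 | -77.6% | -78% |
| Total IgG | 0.22 | 0.2 | -73.0% | -78% |
| Anti-AChR-IgG, 50% reduction | 0.5 | 0.5 | -35.6% | -50% |
| Anti-AChR-IgG | 0.5 | 1 | +0.9% | -50% |
| Anti-AChR-IgG | 0.5 | 2 | +79% | -50% |

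One absolute SD for everyone is a small s at a high titre and a large s at a low one. That is why titre spread decides the size.

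**3. Level reading: error of the imputed value.** Simulation of 3 × 7 participants with one Week 7 value missing in each active arm and arm, baseline and Week 6 as predictors. Assumptions not in the documents: lognormal baselines, anti-AChR-IgG reductions of 50% and 70%, between-participant log-SD 0.25, visit log-SD 0.1 to 0.2. (Protocol 3.2.2 cites about 50% for another anti-FcRn agent.)

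| Baseline log-SD | Draws below zero | Mean error, raw scale with floor (points) | Shift in arm mean (÷ 7) |
|---|---|---|---|
| 0.3 | 2-7% | +0.7 to +3.8 | 0.1 to 0.5 |
| 0.5 | 3-12% | +1.2 to +5.9 | 0.2 to 0.8 |
| 1.0 | 10-19% | +10.6 to +25.5 | 1.5 to 3.6 |
| 1.5 | 17-25% | +63 to +111 | 8.9 to 15.9 |

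At log-SD 1.0, below-median titres carry +21 to +43 points. Log-scale imputation gives +0.3 to +1.9 throughout. Total IgG, simulated in the same way, has +0.6 to +1.1. With baseline as the only earlier value (early loss), the anti-AChR-IgG errors are larger (+46 to +71 at log-SD 1.0) and total IgG has +4.4 to +5.8. Removing the floor alone does not help there: below-median titres then err by -66 to -81 points, with many draws beyond a 100% reduction.

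**4. Power of H03.** One placebo and one 680 mg Week 7 value missing; log effects 0, -0.5 and -0.7 (exp(-0.7) = 0.50, a 50% reduction at 680 mg); effect SD 0.2; within-person SD 0.15; ANCOVA on percent change pooled by Rubin's rules. Ranges cover repeat simulations with somewhat different settings.

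| Baseline log-SD | Raw scale with floor, ANCOVA | Log scale, ANCOVA |
|---|---|---|
| 0.5 | 94-99% | at least 95% |
| 1.0 | 80-87% | at least 95% |
| 1.5 | 52-69% | at least 95% |

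The 90th-percentile standard error at the three spreads is 16, 24-28 and 96-97 points, against 14-15 with log-scale imputation. A rank analysis of the same raw-scale imputed data has power of about 90-98% at log-SD 1.0 and 1.5.

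**The case against.** **The rule may never run.** Multiple imputation needs more than one participant with missing data. On the evidence at blinded review (one COVID case with its own rule, no withdrawals) it would not be used. This stands. A reader might infer that a single missing value is enough to distort H03; the SAP does not support that.

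**Anti-AChR-IgG may not be covered.** SAP 9.1 makes only total IgG primary. SAP 8.3, and 5.4 read with 9.2, point the other way. The question is open.

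**The rank fallback protects the test.** It largely does in simulation, so the ANCOVA power at log-SD 1.0 and 1.5 should not be read as the power of the SAP's whole procedure. But SAP 9.3 states no explicit trigger for the switch, and ranking follows imputation, so the imputed values and the reported ANCOVA estimates stay distorted. The LOCF and observed-case sensitivity analyses also kept power at 98% or more, but they are not the primary analysis.

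**The floor forbids reductions only on a strained reading.** Rounding to observed precision and the wish to avoid negative values both suggest measured levels. A reader might infer that the plan rules out any imputed reduction in IgG; the text permits that reading but does not favour it.

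**The simulations favour the log scale.** Data were generated as lognormal, and Week 6 was the only earlier visit used, although the Protocol's Time and Events tables also schedule anti-AChR on Days 38 and 40. The age, sex, disease-duration and medication covariates were left out. These limits are fair.

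**A lost H03 does not end the MG-ADL analysis.** A reader might infer that it blocks every later claim. MG-ADL change and response are also secondary endpoints, tested at 0.05 without adjustment (SAP 5.4, 9.4.2), though outside the error control of the sequence.

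**Conclusion.** The point holds as a conditional defect in a contingency rule. SAP 5.5 leaves the imputed variable unnamed. On the natural reading, levels, it uses a scale that understates reductions in low-titre participants, and the floor masks this without correcting it. 'Raw scale' is itself inferred, from the absence of a stated transformation and from the need for a floor.

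The effect requires at least two participants with missing data and anti-AChR-IgG within the rule. Its size rests on an assumed titre spread: negligible for H03 at a baseline log-SD of 0.5, ANCOVA power of about 80% at 1.0 and about 55-70% at 1.5, against at least 95% with log-scale imputation. The rank fallback, if invoked, restores about 90-98%. Total IgG, whose primary status is not in dispute, is little affected when Week 6 is observed. The correction is worth making because it is cheap, not because the documents show that the primary result is at risk.

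**What to change.** In SAP 5.5:

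- State that levels are imputed and that percent change is derived afterwards.
- For total IgG, the IgG subclasses and anti-AChR-IgG (where covered), impute log(level) with log baseline and log earlier visits as predictors (TRANSFORM LOG in PROC MI), then back-transform. Drop the zero minimum for these analytes, since every back-transformed value is positive. Keep range limits only for the MG scale totals.
- Reconcile 5.4, 8.3 and 9.1 on whether anti-AChR-IgG is a primary endpoint for the imputation rule.

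The cost is a few sentences, re-validation of the imputation code, and a rule for zero or below-limit results before logs are taken. The spread of screening titres predates treatment and reveals no assignment; it would show which row of the tables applies.

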6. SUBJECT DISPOSITION

6.1. Disposition of Subjects

A summary of subject disposition will be provided by treatment group. This summary will present the number of subjects screened, randomized, included in each analysis set, and the number and percent of subjects:

- Completing the 6-week double-blind treatment period,
- Completing the 12-week post-treatment follow-up period, and
- Not completing the study (with summary of reasons for not completing the study)

The denominator for the percentages of subjects in each category will be the number of subjects in the full analysis set.

Additionally, a summary of disposition will be provided for the OLE by randomized treatment assignment from the double-blind treatment period. This summary will present the number and percent of subjects:

- Completing the 6-week OLE treatment period,
- Completing the 6-week OLE follow-up period, and
- Not completing the OLE

The denominator for the percentages of subjects in each category will be the number of subjects in the OLE analysis set.

No inferential statistics will be generated. Data listings of reasons for study discontinuation and reasons for OLE discontinuation will be provided.

6.2. Extent of Exposure

6.2.1. Duration of Exposure to Study Drug

Duration of exposure to study drug will be defined as (last dose date – first dose date + 1), regardless of temporary interruptions in study drug administration, and will be expressed in days. Duration of exposure to study drug will be summarized using descriptive statistics (sample size, mean, standard deviation, median, Q1, Q3, minimum and maximum) and as the number and percent of subjects exposed at each week.

Summaries will be provided separately for the 6-week double-blind treatment period and the 6-week OLE treatment period by treatment group for the SAF analysis set and the OLE analysis set, respectively. No inferential statistics will be generated.

6.2.2. Adherence with Study Drug Regimen

Adherence to study drug will be defined as the number of doses received divided by the number of doses planned. Adherence will be calculated separately for the 6-week double-blind treatment period and the 6-week OLE treatment period.

Descriptive statistics for adherence (sample size, mean, standard deviation, median, Q1, Q3, minimum and maximum) along with the number and percent of subjects belonging to adherence categories (e.g., <80%, 80% - 90%) will be provided by treatment group for the SAF analysis population and the OLE analysis population, respectively. No inferential statistics will be provided.

6.2.3. Satisfaction with Study Drug Regimen

For each item listed in the first question ("In this study, how bothered have you been by the following:") of the treatment satisfaction questionnaire, the number and percentage of subjects who responded "quite a bit bothered" or "severely bothered" will be summarized. Likewise, for each item listed in the second question ("Regarding the weekly injections, please rate how satisfied you were with the following:"), the number and percentage of subjects who responded "not at all satisfied," "a little satisfied," or "moderately satisfied" will be summarized.

All responses to the treatment satisfaction questionnaire will be listed.

6.3. Protocol Deviations

Major protocol deviations that could potentially affect the efficacy or safety conclusions of the study will be identified prior to database lock and unblinding. Major protocol deviations may include, but are not limited to:

- Randomly assigned subjects who did not satisfy selected inclusion and exclusion criteria;
- Randomly assigned subjects who developed withdrawal criteria during the study but were not withdrawn;
- Subjects who received the wrong treatment or incorrect dose;
- Subjects who received an excluded concomitant treatment;

A listing of all protocol deviations including the deviation designation (major or minor), category, whether it is significant deviation led to an exclusion of a subject from the PP set will be presented in a data listing.

Major protocol deviations will be summarized by deviation category and treatment group. This ongoing clinical study coincides with the coronavirus disease 2019 (COVID-19) global pandemic. Any protocol deviations specifically due to COVID-19 will be summarized separately.

7. BASELINE DATA

7.1. Demographics and Baseline Characteristics

Subject demographic data (e.g., age, sex, race, and ethnicity) and baseline characteristics (e.g., QMG, MG-ADL, MGC, and MG-QOL15r scores, treatments for disease, time since thymectomy, and time from MG onset) will be summarized by treatment group and overall using descriptive statistics (sample size, mean, standard deviation, median, Q1, Q3, minimum and maximum) for continuous data and by the number and percent of subjects for categorical data. The summaries of demographic and baseline characteristics data will be provided for the SAF analysis set. No inferential statistics will be generated. The time from MG onset will be calculated by using (The date of randomization – The start date of the MG collected in the CRF medical history form + 1) / 365. Refer Section [8.4](#) algorithms for the missing or incomplete MG start date.

Additionally, a summary of demographic and baseline characteristics data will be provided for subjects who enrolled in the OLE.

7.2. Medical History

Medical history will be listed.

8. ESTIMAND SPECIFICATION

This SAP is constructed to conform to regulatory guidance. In particular, this section is included as recommended by ICH E9 (R1) Addendum on estimands and sensitivity analysis in clinical trials to the guideline on statistical principles for clinical trials (30 August 2017) and the update November 2019. The scientific question of interest evaluates the potential superiority of RVT-1401 over placebo in the treatment of MG in subjects who meet protocol eligibility criteria.

In accordance with ICH E9 Addendum, the specification of the estimand is included in this SAP with the 4 attributes detailed in ICH E9 Addendum, Section A.3.1.

In accordance with guidance from the ICH E9 (R1) Addendum on Estimands and Sensitivity Analysis in Clinical Trials to the Guideline to Statistical Principles for Clinical Trials (2018), the characterization of the estimand includes the following attributes.

8.1. The Treatment Condition

Blind data review considerations of intercurrent events revealed the potential that infections experienced by some subjects could affect the efficacy scales in important ways, rendering the responses to questionnaire data uninterpretable for protocol purposes.

8.2. The Population of Interest

The population of interest includes qualified subjects who meet eligibility criteria specified in the protocol and who have at least one valid post-baseline measure of IgG.

8.3. The Variable of Interest

For this study, the primary endpoint is IgG level and anti-AChR-IgG with co-primary importance on treatment responsiveness (whether or not subjects are treatment responders) evaluated based on clinical endpoints.

8.4. The Population-level Summary

The population-level summary for this study includes the mean percent change in IgG of patients in the FAS who received RVT-1401 (combined) versus placebo followed by estimates of subjects receiving each dose. Response data from efficacy questionnaires will include mean changes, mean percent changes, and responder analysis as defined under variables of analysis.

